Collaborators/Co-Investigators/Protocol Contributors	
Name: [name] Address: [name] UoL job title: Senior Lecturer in Clinical Psychology [contact] Email: [contact]
 
Research supervisor for the doctoral student
 
Name: [name] Address: [name] UoL job title: Senior Clinical Academic, Co-Director of the Trent Doctoral Programme in Clinical Psychology [contact] Email: [contact]
 
Research supervisor for the doctoral student

Student	
[name], doctoral student on Trent Doctorate of Clinical Psychology (DClinPsy). [contact]. Email: [contact]

FUNDER DETAILS

FUNDER(S)	FINANCIAL AND NON FINANCIAL SUPPORT GIVEN
Higher Education England	Student research – no specific project funding. This research project is being completed in partial fulfilment of the Doctorate in Clinical Psychology programme, funded by Health Education England

STUDY SUMMARY

Study Title	The Nurtured Heart Parenting Intervention for Children's Behavioural Problems: A Single Case Design
Study Design	The study will use a non-concurrent across-participant multiple baseline A-B single case design.
Study Participants	Participants will be parents/carers of children who have been referred to National Health Service (NHS) specialist children's services. Participants will be recruited from the waiting lists of children's services at two NHS trusts in the East Midlands.
Eligibility Criteria	
Inclusion criteria: the parent/carer identifies their child's behaviour as problematic; the child's behavioural problems are one of the primary presenting problems; and the referred child is aged between three and eleven years old.
 
Exclusion criteria: the child has a diagnosis of developmental delay or learning disability; the family is receiving active multi-agency involvement; and the participant is unable to read/speak English fluently.

Planned Sample Size	The planned number of participants is six.
Study Duration	
The duration of the intervention for participants is 13 weeks: 3 weeks baseline data collection, 6 weeks intervention, post-intervention follow-up 4 weeks after intervention completion. Total participant duration from first contact with participants will be approximately 16 weeks.
 
The total expected duration of the study is 13 months. Planned start date: February 2022 (dependant on approval by ethics committee). The research will be submitted in the form of a thesis in partial fulfilment of the requirements for the Trent Doctorate in Clinical Psychology. Planned submission date: February 2023.

Objectives	
The primary research question is: When delivered in a guided self-help format, is the NHA effective in reducing parent-reported children's behavioural problems?
 
The secondary research questions are:
 
 1. When delivered in a guided self-help format, is the NHA effective in: 
 a. reducing negative parenting practices? b. increasing parental reflective functioning? 2. To what extent is the NHA a feasible and acceptable intervention for parents of children with behavioural problems when delivered in a guided self-help format?
Outcome Measures	Measures: Brief Problem Monitor (BPM; Achenbach et al., 2011), Psychological Outcomes Profiles (PSYCHLOPS; Ashworth et al., 2009), Multidimensional Assessment of Parenting Scale (MAPS; Parent & Forehand, 2017); Parental

	
Reflective Functioning Questionnaire (PRFQ; Luyten et al., 2017), Warwick-Edinburgh Mental Well-Being Scale (WEMWBS; Tennant et al., 2007)
 
A semi-structured change interview (based on Rodgers and Elliott (2015) will be completed with participants 4 weeks post-intervention.

Data Analysis	
Visual analysis and calculations of reliable and clinically significant change will be used to analyse the quantitative data. Framework analysis as outlined by Gale et al. (2013) will be used to analyse the change interviews.

KEY WORDS

Nurtured Heart Approach; parenting; child behavioural problems; single case design.

Table of Contents

SIGNATURE PAGE.....	3
STUDY/TRIAL CONTACTS.....	4
FUNDER DETAILS.....	4
STUDY SUMMARY	5
KEY WORDS	6
LIST OF ABBREVIATIONS	9
STUDY MANAGEMENT.....	10
ROLE OF STUDY SPONSOR AND FUNDER.....	10
STUDY BACKGROUND and RATIONALE	10
Development of the problem	10
Interventions	11
STUDY OBJECTIVES AND PURPOSE	12
PURPOSE AND PRIMARY OBJECTIVES.....	12

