The Parental Reflective Functioning Questionnaire (PRFQ) will be used to assess parental reflective functioning. The PRFQ has not been validated by developers for parents of children aged six to eleven (Luyten et al., 2017). However, there is preliminary evidence that the measure is valid in children up to the age of ten (Pazzaglia et al., 2018). Consequently, the PRFQ will be used for participants of this study as, despite the limited validation in age range of the PRFQ, it is the only measure in existence that captures parental reflectivity.

Ideographic measure

An ideographic measure is included to capture parents' perception of the problems and assess any change. The Psychological Outcomes Profiles (PSYCHLOPS; Ashworth et al., 2009) items will be generated with each participant at the beginning of the baseline phase. The PSYCHLOPS is more proportionate than the Personal Questionnaire (Elliott et al., 2016) as it focuses on two problem areas rather than ten; this will reduce the time burden on participants during the generation of items and completion of the measure.

General wellbeing measure

Understanding general wellbeing is important as it is likely to impact parenting behaviour. The Short Warwick-Edinburgh Mental Well-Being Scale (SWEMWBS; Tennant et al., 2007) will be used instead of the General Health Questionnaire (GHQ-12; McCabe et al., 1996) because the GHQ-12 primarily screens for psychopathology whereas the SWEMWBS also captures positive aspects of wellbeing.

Change interview

One month post intervention the participants will also be asked to take part in a semi-structured change interview (Rodgers & Elliott, 2015). The purpose of the interview is to capture parents' views of any changes resulting from their participation in the NHA intervention. The addition of this qualitative data will allow for a more comprehensive evaluation of the intervention.

STUDY DESIGN

The study proposes using a non-concurrent across-participant multiple baseline A-B single case design. The baseline period (A) precedes the intervention period (B), where the NHA is delivered in a guided self-help format over six weeks. Data will be collected using psychometric measures and post-intervention data

collection will also include a qualitative semi-structured change interview. Full details are given below in "Study Procedure".

DATA ANALYSIS

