Visual analysis is the suggested method of analysing single case design data (Barlow et al., 2009) and consequently will be used to analyse the data resulting from this research. The data will be visually represented on graphs and examined for trends in the data indicating if and when change has occurred across the process measures for the three variables of interest. The data will also be analysed to establish if any changes are reliable and clinically significant. Assessment of reliable change identifies if change is genuine or resulting from measurement error; this will be calculated using the Reliable Change Index (Jacobson & Truax, 1991). If changes prove reliable, they will be analysed for clinical significance (Jacobson & Truax, 1991). The change interviews will be transcribed verbatim by the doctoral student and analysed using framework analysis as outlined by Gale et al. (2013). NVivo will be used to conduct the framework analysis.

Data analysis will be completed by the doctoral student with support from the research supervisors (CI and collaborator). No interim analysis are planned.

STUDY SETTING

The study will be run across two mental health trusts in the East Midlands. The specialist children's services (Child and Adolescent Mental Health Service; CAMHS) within [redacted NHS Trust] will be the primary study site. The CAMHS service consists of four locality teams across the county, all of which work together to form one service. The population being recruited from will be parents/carers of children on the waiting lists for these services. Recruitment will be supported by staff within these services who are aware of the research project and its aims.

The secondary study site will be CAMHS services within [redacted NHS Trust]. Recruitment will only occur in the secondary study site if it has not been possible to recruit sufficient participants from the primary study site. Again, recruitment will be focused on parents/carers of children on the waiting lists for CAMHS services and will be supported by clinical psychologists within CAMHS who are aware of the research project and its aims.

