The process for obtaining participant informed consent will be in accordance with the REC guidance, and Good Clinical Practice (GCP) and any other regulatory requirements that might be introduced. The investigator or their nominee and the participant shall both sign and date the ICF before the person can participate in the study. Participants will be able to sign the ICF electronically or can sign, scan and send back the form electronically. One copy of the ICF will be kept by the participant, one will be kept by the research team, and a third will be retained in the referred child's medical records. It will be explained to the potential participants that participation in the research study will not impact the treatment as usual that they receive from the service for which the referred child is on a waiting list. Participants will be given the contact details of the research team should they have any further questions. Should there be any subsequent amendment to the final protocol, which might affect a participant's participation in the trial, continuing consent will be obtained using an amended consent form which will be signed by the participant. Capacity will be assumed for all participants as they will be adults (over the age of 18).

[figure not shown]
STUDY PROCEDURES/REGIMEN

STUDY FLOWCHART

Below are the study flowcharts written for the participant. The first explains the process of recruitment, the second explains participation in the intervention.

Flowchart

Recruitment.

Baseline Phase

The researcher contacts the participant twice per week to collect information using questionnaires (also called measures). This phase is likely to last three weeks but may be slightly longer.

The participant decides they do not want to continue taking part in the study, informs the researcher and is withdrawn from the study.

The participant no longer meets the eligibility criteria for the study. The researcher informs them and the participant is withdrawn from the study.

The participant completes the baseline phase and continues to the intervention phase.

Intervention Phase

The participant will be sent one chapter of the workbook to read each week. The researcher contacts the participant once a week to collect information using questionnaires and discuss the chapter. This phase lasts six weeks.

The participant decides they do not want to continue taking part in the study, informs the researcher and is withdrawn from the study.

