The participant no longer meets the eligibility criteria for the study. The researcher informs them and the participant is withdrawn from the study.

The participant completes the intervention phase and continues to the follow-up phase.

Follow-up Phase

The researcher will contact the participants to complete the questionnaires for the last time and arrange a follow-up interview with an independent researcher. The follow-up interview is the participant's chance to give feedback on the intervention and how you found it.

The participant decides they do not want to continue taking part in the study and informs the researcher.

After taking part in the interview, the participant has completed the study and will be sent an overview of the research unless they have opted out.

STUDY REGIMEN

The screening procedure is outlined above in the eligibility, recruitment and consent sections.

Baseline phase

Following informed consent, participants will begin the baseline phase. During the baseline phase, participants will be contacted twice a week by phone by the doctoral student to collect the data. The table below shows the frequency of administration for each measure throughout the study. The exact timing of phone calls will be organised with each participant around their availability and the availability of the doctoral student.

The necessity to complete multiple measures will be made clear to participants both in the initial conversation and PIS. If participants do not consistently complete the measures, the researcher will speak to the participant to identify why and explain the impact on the research. If measures continue not to be completed during the baseline phase, participants may be withdrawn from the study.

If stability is not achieved on any variable, participant data will be considered on a case-by-case basis. Lack of stability likely to undermine the validity of subsequent results may result in participants being withdrawn from the study. However, because each participant acts as their own control, a limited amount of variability may not have a significant impact on the study (Kratochwill et al., 2010).

Intervention phase

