Multidimensional Assessment of Parenting Scale (MAPS)	✓	✓	✓	✓	✓	✓		✓		✓		✓		✓		✓		✓	✓
Parental Reflective Functioning Questionnaire (PRFQ)	✓	✓	✓	✓	✓	✓		✓		✓		✓		✓		✓		✓	✓
Brief Problem Monitor (BPM)	✓	✓	✓	✓	✓	✓		✓		✓		✓		✓		✓		✓	✓

SCHEDULE OF PROCEDURES

Procedures	Sessions			
	Screening	Baseline (weeks 1-3)	Intervention (weeks 4-9)	Follow up (week 13)
Informed consent	x			
Demographics		x		
Measure collection		x	x	x
Intervention			x	
Change interview				x

WITHDRAWAL

Participants may be withdrawn from the trial either at their own request or at the discretion of the investigator (with input from the whole research team). The participants will be made aware that this will not affect their future care. Participants will be made aware (via the information sheet and consent form) that should they withdraw the data collected to date may not be erased in accordance with the University's Research Privacy Notice and information given in the Participant Information Sheet and may still be used in the final analysis.

Participants who withdraw prior to starting the intervention will be replaced. After starting the intervention phase, replacement of participants will be considered on a case-by-case basis depending on individual circumstances. If a participant withdraws before the start of the intervention phase, they will not receive the self-help workbook, but will be made aware that they can purchase the book themselves.

ETHICAL AND REGULATORY CONSIDERATIONS

ASSESSMENT AND MANAGEMENT OF RISK

If information is disclosed during the study that could pose a risk of harm to the participant or others, the researcher will discuss this with the CI and where appropriate report accordingly.

Risks will be managed in accordance with each trust's safeguarding policy. The Health and Care Professions Council (HCPC) practitioner psychologist guidance will also be adhered to. During participation in the study, the doctoral student may become aware of harm being caused to the referred child or other children. If a disclosure or concerns about a child are raised, the trust policies will be followed and the referred child's usual care team and the chief investigator will be informed at the earliest possible opportunity.

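### The design is called multiple baseline, but every participant is scheduled the same three-week baseline, so the intervention effect cannot be separated from week since entry unless the shape of the time effect is assumed

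*Combined protocol and SAP*

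**What the plan says.** The Study Summary (Study Design) states: "The study will use a non-concurrent across-participant multiple baseline A-B single case design". The Study Design section repeats the label.

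The timetable is common to everyone. Study Duration gives "3 weeks baseline data collection, 6 weeks intervention, post-intervention follow-up 4 weeks after intervention completion". The table of measure frequency shows six baseline readings in weeks 1 to 3 and six weekly intervention readings in weeks 4 to 9. The Schedule of Procedures uses the same weeks. The only flexibility is in the participant flowchart, which says of the baseline: "This phase is likely to last three weeks but may be slightly longer". It gives no length, trigger or method of assignment.

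Under Data Analysis the graphs are to be "examined for trends in the data indicating if and when change has occurred across the process measures for the three variables of interest", followed by reliable and clinically significant change. No comparison between participants with different baseline lengths is described. On unstable baselines, Study Regimen says: "If stability is not achieved on any variable, participant data will be considered on a case-by-case basis". Size of sample aims for six participants, cites three as the minimum for showing an experimental effect, and says that a fall to three would leave the findings valid.

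**The concern.** In a multiple baseline design across participants, some participants are still in baseline when others, at the same time since entry, have started the intervention. That overlap distinguishes an intervention effect from change that would have come anyway. Here nobody is scheduled to be in baseline after week 3, so there is no overlap.

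The primary question is causal: whether the programme is effective in reducing parent-reported behavioural problems. Parents join from a waiting list having identified the behaviour as a problem, and they answer the Brief Problem Monitor (BPM) 13 times (6 + 6 + 1). Regression towards the usual level, natural course and repeated measurement could each produce a fall over the weeks. The alternative is hardest to rule out for a benefit that builds slowly over one chapter a week. The label would lead a reader to credit a control that the schedule lacks, and the assurance about three participants rests on experimental control of that kind.

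**Working it through.** **The plan's own figure.** 3 + 6 + 4 = 13 weeks, as stated. One schedule accounts for the whole stated duration, with no room for a stagger.

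**Is the effect estimable?** Write the score of participant *i* in week *w* since entry as *a(i)* + *b(w)* + *δ·x(i,w)* + error, where *x* is 1 during intervention and each week has its own free effect. On the planned schedule *x* = 1 exactly when *w* is 4 to 9, for everyone. So *x* is the sum of the columns for weeks 4 to 9, and *δ* cannot be estimated. No drift is assumed. Counting columns as participants + (weeks − 1) + 1, follow-up left out:

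| Schedule | Participants | Columns | Rank |
|---|---|---|---|
| 3 weeks for all | 3 | 3 + 8 + 1 = 12 | 11 |
| 3 weeks for all | 6 | 6 + 8 + 1 = 15 | 14 |
| 3 weeks for all | 12 | 12 + 8 + 1 = 21 | 20 |
| 3/4/5 weeks, two each | 6 | 6 + 10 + 1 = 17 | 17 |

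Including the follow-up reading changes nothing: for six participants on the common schedule the rank is 15 of 16.

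**What would a stagger buy?** Assume independent errors with unit within-person SD and free week effects. SE = 1/√RSS, where RSS is what remains of the intervention term after regression on the participant and week columns. With 3/4/5-week baselines:

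- Immediate shift: SE 0.574 SD (six participants), 0.811 SD (three).
- Benefit building linearly to full size at the sixth intervention week: SE 1.718 SD (six), 2.430 SD (three).
- Effect needed for 80% power, two-sided 5%, six participants: 2.80 × 0.574 = 1.6 SD if prompt; 2.80 × 1.718 = 4.8 SD if gradual.

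**How far could drift alone move the phase means?** Take reading days as 0, 3, 7, 10, 14, 17 (mean 8.5) and 24, 31, 38, 45, 52, 59 (mean 41.5). The phase means are 33 days, or 4.7 weeks, apart. A linear drift of *d* points a week with no treatment effect therefore shifts the A-B difference by 4.7*d*.

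The documents give no drift figures, so what follows is an illustration on assumed values. Let the score at entry be elevated by *E* within-person SDs, decaying as *E* × 0.5^(days/(7*h*)) with half-life *h* weeks, and no treatment effect. The check tested is a one-sided 5% test of a common baseline slope with participant intercepts:

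| *E* (SD) | *h* (weeks) | Baseline minus intervention mean (SD) | Drift detected: 1 / 3 / 6 participants |
|---|---|---|---|
| 1.0 | 2 | 0.53 | 11% / 20% / 31% |
| 1.0 | 4 | 0.45 | 8% / 12% / 17% |
| 1.5 | 2 | 0.80 | 15% / 33% / 53% |
| 1.5 | 4 | 0.67 | 10% / 18% / 27% |

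On these assumptions the six-reading baselines give only a partial check against drift, and a weaker one if numbers fall to three.

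**The case against.** The strongest reply is that the rank deficit appears only when every week has its own free effect, a model the protocol does not propose. Any A-B series with a common start fails that test. Visual analysis looks for an abrupt change at week 4, which is informative if drift is smooth. For six participants (follow-up left out), the planned schedule then gives a prompt-shift SE of 0.48 SD with a linear trend and 0.54 SD with a quadratic one, against 0.45 and 0.46 SD with the 3/4/5-week stagger. For prompt change under smooth drift the stagger gains little. For gradual benefit under linear drift it improves the SE from 1.31 to 0.90 SD, still imprecise. All of this stands, but it depends on assuming a smooth time effect, and the multiple baseline label exists to avoid that assumption.

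Second, the flowchart permits unequal baselines. One four-week baseline among six would break the exact aliasing, but with an SE of 0.90 SD resting on a single case. If instability prompted the extension, it would also depend on the outcome.

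Third, there are other protections: differing entry dates guard against a shared calendar event, baseline stability is reviewed, cases are replicated, each parent serves as their own control, and a student not previously involved conducts the change interview. These have value, but none separates intervention from time since entry, and the stability review has no criterion.

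Finally, the drift values are assumed, and the sample-size section does not mention staggering. The first is why the values serve only as illustration. On the second, that section speaks of demonstrating an experimental effect, which supports reading it as relying on experimental control.

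**Conclusion.** The concern holds and should be settled before the first enrolment, because staggering cannot be added once participants have started the intervention. The label claims a control that no schedule in the protocol provides. For the schedule as written, the aliasing of intervention with week since entry is exact (rank 14 of 15 for six participants, 11 of 12 for three) and needs no assumption about drift. It is lifted only by assuming the shape of the time effect. The size of any resulting bias cannot be derived from the documents: the 0.45 to 0.80 SD range is conditional on the assumed entry elevation and half-life. The standard errors assume independent readings with unit within-person SD.

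**What to change.** Choose one of the following before the first enrolment.

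**(a) Keep the label and supply the stagger.** Pre-specify different baseline lengths, for example 3, 4 and 5 weeks (6, 8 and 10 readings) with two participants each. Assign them at random and not in response to data, and give a replacement participant the vacated length. Replace the open-ended flowchart wording with these lengths, and align the Study Summary, measure table and Schedule of Procedures. State in Data Analysis that the visual analysis will compare across tiers whether BPM change follows the start of intervention and not time since entry. State also that a one-week stagger helps mainly with prompt change, so causal wording on a gradual change stays limited.

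Cost: baseline calls rise from 6 × 6 = 36 to 2 × (6 + 8 + 10) = 48, which is 12 more. Two families wait one week longer and two wait two weeks longer, so the approximate 16 weeks from first contact becomes up to about 18. Each call carries the BPM, the reflective functioning questionnaire and the parenting scale. The protocol calls the full parenting scale a time burden, though a short form is planned. Longer baselines raise the risk of drop-out and of withdrawal under the rule "If measures continue not to be completed during the baseline phase, participants may be withdrawn from the study", with replacement inside a 13-month timetable. An ethics amendment may be needed.

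**(b) Change the wording only.** Replace multiple baseline with replicated A-B, limit the causal wording on effectiveness, and qualify the statement in Size of sample that three participants would suffice. This costs nothing beyond the edit.
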